**STUDY SUMMARY**

Study Title	Discovering the molecular signatures of cancer PROMotion to INform prevention (PROMINENT): Smoking Cessation Study
Internal ref. no. (or short title)	PROMINENT: Smoking Cessation Study (Sponsor Reference Number: NHS002126)
Study Design	Observational study
Study Participants	Current smokers, aged ≥55 years old, no prior history of cancer
Planned Size of Sample (if applicable)	150 - 250
Follow up duration (if applicable)	Between 3 and 12 months after recruitment
Planned Study Period	3rd June 2024 – 31 st May 2027
Research Question/Aim(s)	Study the impact of smoking cessation on the molecular architecture of human buccal and nasal cells.

**FUNDING AND SUPPORT IN KIND**

[figure not shown]
FUNDER(S) (Names and contact details of ALL organisations providing funding ± support in kind for this study)	FINANCIAL AND NON-FINANCIAL SUPPORT GIVEN
Cancer Grand Challenge - Funded by Cancer Research UK (CRUK) and National Cancer Institute (NCI), project grant reference: CGCATF-2021/100007	Financial support awarded (Cancer Grand Challenge grant)

**KEY WORDS:**

Lung cancer, smoking cessation, cancer prevention

PROMINENT Smoking Cessation Study

STUDY FLOW CHART

### 1. BACKGROUND & RATIONALE

Tobacco smoking is known to increase the risk of cancer in both humans and mouse models. The causal link between smoking and tumours of the lung (1), and up to 14 other cancer types (1, 2), has been well established. While there is compelling epidemiological evidence to link tobacco smoking with cancer risk, the underlying biological mechanisms are not well understood. Importantly, we do not understand how smoking impacts the phenotypes of normal tissues and how it promotes cancer development.

To determine the specific role of tobacco smoking in tumour promotion, we will conduct an observational study to investigate the effect of changes in smoking on tissue biology. Specifically, the PROMINENT Smoking Cessation Study will collect serial samples of buccal and nasal cells from volunteers undergoing a smoking cessation lifestyle modification. The underlying hypothesis is that through the comparison of samples obtained prior to the intervention and at subsequent time points thereafter, we will be able to observe differences in the molecular and clonal architecture of normal tissues. These changes will help us understand the mechanisms by which smoking promotes cancer development and could help identify molecular targets for prevention.

This key line of investigation will identify the changes that occur in human buccal and nasal cells upon smoking cessation, which may underlie the observed decreased risk of cancer development observed in people who cease smoking. A clear contribution of tobacco smoking to the mutation rate in certain tissues has been firmly established (3). However, whether it acts exclusively through a contribution to the somatic variation of tissues, or (in addition, or exclusively) as promoters of tumorigenesis is not well understood. In the case of smoking, there is clear evidence of its role in the development of mutations that are drivers of tumours in the lung and other organs. However, recent evidence suggests that quitting smoking promotes replenishment of the bronchial epithelium from mitotically quiescent cells that have avoided tobacco-induced mutagenesis (4).

In addition, there is growing interest in the effects of e-cigarettes on health. Although now widely used for smoking cessation, nicotine and other compounds contained in e-cigarettes can induce oxidative stress in human bronchial and lung epithelial cells resulting in inflammation, cytotoxicity and increased endothelial cell permeability (5). Therefore, it is of public health interest to understand the physiological impact of e-cigarettes. Within this study we will be able to assess the impact of smoking cessation on normal cells in those who go on to use e-cigarettes versus those who use other means. Buccal cells will be obtained through oral rinse which has also been shown to be an effective method for providing cells amenable to molecular profiling (6).

The nasal mucosa has a strong functional and immunological relationship with the lungs. The nasal mucosa may therefore act as a surrogate for the bronchial epithelium, without the need for invasive tests such as bronchoscopy or induced sputum. We will also include nasal sampling in this study.

### 1.1. Manchester Lung Health Check Programme

The study will recruit people who currently smoke and who attend the Greater Manchester Lung Health Check (GM-LHC) programme, which is a community-based lung cancer screening service located in highly deprived areas of Greater Manchester (<https://mft.nhs.uk/lunghealthcheck/>). People who have ever smoked, aged 55-74 years, and resident in areas covered by the service, are invited to have a Lung Health Check (LHC). The LHC includes an assessment of respiratory symptoms, measurement of lung function (spirometry), smoking cessation support, and an assessment of cardiovascular and lung cancer risk. Those at higher risk of lung cancer, as calculated by a risk prediction model e.g. PLCOM2012 (threshold  $\geq 1.51\%$  six-year risk) or LLPv2 (threshold  $\geq 2.5\%$  five-year risk), are offered an immediate low dose CT (LDCT) scan in a co-located mobile CT scanner. Screening outcomes from the GM-LHC have previously been published (7, 8).

### 1.2. Manchester CURE (stop smoking) Project

Manchester has implemented a vanguard programme of hospital-based tobacco-dependency treatment services. The Manchester CURE project (*Conversation-Understand-Replace-Experts/Evidence-base*) has translated the published evidence base of the effectiveness of hospital-based tobacco dependency treatment (the Ottawa Model of Smoking Cessation and randomised controlled trial data) into a resilient, sustainable, and scalable real-world clinical service model (9-12). The CURE team approach every patient that smokes and offers a review of pharmacotherapy, specialist behaviour change support, and motivational interviewing. A key part of this specialist consultation is also offering and agreeing a treatment and support plan after discharge. The CURE team offer ongoing medications and support following discharge, through regular outpatient consultations (face to face or telephone) for 12 weeks or referral to community services for ongoing support. In a pilot of the CURE project the self-reported 12 week quit rate for current smokers was 22% (13). The CURE project has expanded its reach beyond the inpatient pathway to provide outpatient services and tobacco dependency treatment within the Greater Manchester Lung Health Check Programme. The same core principles are maintained within these programmes which include opt-out referral with immediate on the day specialist assessment to commence treatment and agree a further support package beyond the initial assessment. The clinical team will ask current smokers who wish to quit and are eligible for screening whether they would be interested taking part in the study. Those who express an interest will discuss the study with a member of the research team.

## 2. RESEARCH QUESTION/ AIM(S)

**Main research question:** What is the impact of smoking cessation on the molecular characteristics on nasal and buccal cells, and does exposure to e-cigarettes lead to specific molecular changes in these tissues?

### 2.1. Objectives

#### 2.1.1. Primary

- Understand how smoking cessation affects normal nasal and buccal cells to modify tumorigenesis risk.
- Understand how e-cigarettes affects normal nasal and buccal cells compared to individuals who continue to smoke and individuals who have stopped smoking without the use of e-cigarettes.

#### 2.1.2. Secondary

- Compare molecular changes with clinical characteristics from lung cancer screening.
- Assess the effectiveness of smoking cessation interventions in a screening cohort

### 2.2. Outcome measures

- Differences in molecular signals before and after smoking cessation
- Differences in molecular signals in those who do and do not use e-cigarettes

### 3. STUDY DESIGN and METHODS of DATA COLLECTION AND DATA ANALYSIS

#### 3.1. Study design

This study is an observational cohort design.

#### 3.2. Data collection

A study questionnaire will be completed at baseline, following consent. This will include demographic information such as socioeconomic status, ethnicity, smoking behaviour, education and employment status in order to describe the sample. Further data collection will be undertaken at timepoints 2 and 3 where smoking status will be updated and information about quit attempts, use of nicotine replacement therapies and e-cigarette use recorded.

The questionnaire will be completed by the participant at the study visit or over the telephone, with a member of the research team recording the participant's response to questions. This may be done electronically (an electronic device will be available on site for this purpose) or on paper.

Consent will also be sought to access relevant data from the participant's medical records (primary or secondary care) which will be transferred to and securely stored on a research database at Manchester University NHS Foundation Trust (MFT). This will include information from the LHC and the outcome of screening (result of the LDCT scan). For those individuals diagnosed with cancer details of the type, stage and treatment will be recorded. Only authorised members of the research team at MFT will be allowed to access participants' medical records.

A personal data collection form will also be completed at the first visit. This will ask for details such as their name, NHS number, date of birth, gender and contact details. This form will be used to develop a research database which will be used to track participants' scan results, arrange telephone calls and the follow-up visit, confirm co-morbidities and record data collected from participants' medical records. This database will be stored on NHS Trust servers and will only be accessed by the research team based at MFT.

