#### 3.3. Data analysis

The clinical cohort will be stratified according to smoking status at timepoint 3 into a Quit Cohort (stopped smoking for 3 months or more at the time of sample collection) and a Smoking Cohort (smoked within 3 months of sample collection). Analysis of laboratory data will be stratified over time (baseline compared to timepoint three) and according to final cohort categorisation.

Machine learning algorithms will be developed to integrate across all of the features of the multi-omics analysis of normal tissues, to identify the combinations of parameters that contribute most to cancer risk. We will integrate salient features of the dynamics of tissue perturbation by tumour promoters including the clonal structure of tissues, protein and gene expression patterns, and differences in the pattern of infiltration of immune cell populations. In order to understand the association between these features and carcinogenesis. We will study whether they can be used to discriminate between groups of samples before or after intervention. We propose an analysis that is organized in logical steps with increasing degrees of complexity.

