**PROMINENT Smoking Cessation Study**

First, we will conduct univariate group comparison analysis to assert any outstanding correlations feature-wise. But the high-dimensionality of the feature space will require a meaningful low-rank feature representation. For some features a domain-specific dimensionality reduction method can be applied, e.g., gene expression features may be encoded as eigengenes using gene co-expression network analysis. More general linear dimensionality reduction methods like principal component analysis (PCA, unsupervised) or linear discriminant analysis (LDA, supervised) will complete the study of the feature space structure. From this analysis we will derive a compendium of features that convey the most information about the difference in the risk of tumour development across exposures linked to cancer or with lifestyle changing interventions.

We will then use supervised classification procedures (e.g., logistic regression and/or the more sensitive gradient boosting models) to combine these features into explanatory models able to weigh the relative contribution of each feature to the carcinogenic process. The aim of this part of the analysis is to further include putative additive effects as well as non-trivial feature interactions in relation to carcinogenesis. The labels of the training and test instances will be assigned based on the carcinogenesis endpoints specified above. Models able to discriminate between normal tissue before and after intervention will be built and evaluated. Cross-validation and other statistical information criteria (e.g., AIC) will be employed for model evaluation. In the case of gradient boosting models, local feature explanations (e.g., Shapley Additive Explanations or SHAP) will be derived to render the models interpretable.

The outcome of this statistical analysis will serve as a tool for data integration to learn how combinations of different features predict risk and exposure to promoters. Although we do not intend to translate these models to clinical predictive tools, some of the outcomes of this key line of investigation may well lead into some applicable knowledge for risk prediction. Given that the main goal of these models is to help us learn the molecular features of tumour promotion, we will put special emphasis in developing models that are interpretable, using approaches such as SHAP values that we have used before.

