### 5.2. Sampling

#### 5.2.1. Size of sample

The study is exploratory; the primary aim is to analyse paired sequential samples from current smokers who successfully quit smoking. Based on our data, approximately 20% of current smokers are able to quit therefore to ensure a minimum of 50 paired samples, up to 250 current smokers will be recruited at baseline. We also aim to recruit paired samples from participants who are current smokers at baseline and at timepoint 3.

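### The Quit v Smoking and e-cigarette contrasts compare self-selected groups, but the protocol gives the baseline data no stated role in adjusting them

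*Protocol*

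**What the plan says.** Section 3.1 states the design: "This study is an observational cohort design". Section 3.2 says that the baseline questionnaire records "socioeconomic status, ethnicity, smoking behaviour, education and employment status in order to describe the sample". Date of birth and gender come from a separate personal data form, and Lung Health Check results come from medical records.

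Section 3.3 sets the groups: "The clinical cohort will be stratified according to smoking status at timepoint 3 into a Quit Cohort" (no smoking for three months or more) and a Smoking Cohort (smoked within three months). It continues: "Analysis of laboratory data will be stratified over time (baseline compared to timepoint three) and according to final cohort categorisation". The analysis then goes in steps. The first is: "First, we will conduct univariate group comparison analysis to assert any outstanding correlations feature-wise". Dimension reduction follows, and then: "We will then use supervised classification procedures (e.g., logistic regression and/or the more sensitive gradient boosting models) to combine these features". The features meant are molecular and tissue features. No step names a participant characteristic as an adjustment variable.

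Section 5.2.1 says that "the primary aim is to analyse paired sequential samples from current smokers who successfully quit smoking", and adds that pairs from people still smoking at timepoint 3 are also sought, without giving a number. The second primary objective in section 2.1.1 compares e-cigarette users with continuing smokers and with people who stopped without e-cigarettes. Section 5.1.1 admits two recruitment streams: Lung Health Check attendees aged 55 or over who meet a lung cancer risk threshold, and CURE attendees aged 40 or over with no risk threshold.

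**The concern.** Whether a participant falls in the Quit Cohort, the Smoking Cohort or the e-cigarette group depends on that person's own behaviour after baseline. Amount smoked, age, deprivation and recruitment route may plausibly affect both that behaviour and how nasal and buccal cells change over the following months. If so, a difference in change between groups mixes the effect of stopping or vaping with the effect of who stops or vapes.

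Molecular features are correlated, so one imbalance can shift many of them together and look like a coherent signature. Correction for multiple testing does not remove such a bias. Features picked out at the univariate step may also carry it forward into the classifiers and their SHAP rankings.

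**Working it through.** **The plan's own figure.** Section 5.2.1 assumes a 20% quit rate and a minimum of 50 quitter pairs: 50 / 0.20 = 250, which reproduces the stated maximum. It rests on an expected count of quitters, not on a between-group contrast. The protocol gives no SD, effect size or power from which a bias could be scaled.

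**Which contrasts are exposed.**
- Before/after within quitters: each person is their own control, so stable additive differences (ethnicity, education, past exposure) cancel. Elapsed time and laboratory batch do not cancel.
- Quit v Smoking difference in change: this is needed to separate cessation from elapsed time and batch. It compares self-selected groups. Pairing still removes differences in level, but not factors that affect the change itself.
- E-cigarette users v continuing smokers v quitters without e-cigarettes: these groups are self-selected too, and this is a primary objective.

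**Source of imbalance visible in the protocol.** Under section 5.1.1, age range and lung cancer risk differ by recruitment route. If quit rates or e-cigarette use also differ by route, group is confounded with both. Section 3.3 does not mention route.

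**Illustrative size.** The inputs below are assumptions, apart from the counts, which use 20% of 250 with full retention (50 v 200 pairs).
- Standard error of the difference in change, in SD units of change: sqrt(1/50 + 1/200) = 0.158.
- A baseline covariate that differs by d SD between groups and correlates rho with the change gives a bias of rho × d.
- Error rate of a nominal 5% two-sided test under no true difference: P(Z > 1.96 − bias/SE) + P(Z < −1.96 − bias/SE).

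| rho | d | bias (SD) | bias/SE | error rate |
|---|---|---|---|---|
| 0.2 | 0.2 | 0.04 | 0.25 | 5.7% |
| 0.3 | 0.4 | 0.12 | 0.76 | 11.8% |
| 0.4 | 0.6 | 0.24 | 1.52 | 33% |

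At the lower planned size of 150 (30 v 120 pairs), the SE is sqrt(1/30 + 1/120) = 0.204, and the same biases give 5.4%, 9.0% and 21.7%. The error rate is lower only because the test is weaker; the bias is unchanged.

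**Adjusting for the timepoint 1 value.** This is not a neutral remedy in non-randomised groups. If the groups differ at timepoint 1 by delta and would otherwise change in parallel, a model conditioning on timepoint 1 shows a spurious difference of (1 − r) × delta, where r is the within-person correlation. With assumed delta = 0.3 SD and r = 0.5, that is 0.5 × 0.3 = 0.15 SD, larger than the middle example above. The change score is therefore the safer main outcome here.

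**The case against.** The strongest reply is that choice of covariates is commonly left to a statistical analysis plan, and none is shown. A missing covariate list would indeed be no finding. The protocol does more than stay silent, however: it states a purpose for the questionnaire data, and that purpose is description. An analysis plan that used them for adjustment would go beyond the stated purpose.

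Other parts of the reply stand and limit the point.
- A reader might infer that the protocol restricts these data to description. It does not say so. Description is the only use stated, other uses are not excluded, and the phrase does not cover age, sex or recruitment route. The secondary objective relating molecular changes to screening characteristics (section 2.1.2) shows that clinical data may enter analyses, though it is not confounder adjustment.
- A reader might take univariate to mean unadjusted. In context it may mean one feature at a time, and it is only the first step. The later steps are multivariable, but across molecular features.
- A reader might conclude that the whole cessation analysis is confounded. The paired analysis in quitters, which section 5.2.1 calls the primary aim, is protected against stable differences in level. Section 3.3 can also be read as before/after within each cohort.
- The study calls itself exploratory. That excuses modest power, but not attributing to cessation what is due to who quits.

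**Conclusion.** The point holds for the between-group contrasts: the Quit v Smoking difference in change and the three-way e-cigarette comparison. As written, the protocol gives participant characteristics no adjusting role in either, although both compare self-selected groups drawn from two differently defined recruitment streams. It is worth correcting because the relevant baseline data are largely collected already.

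The size is not established. The error rates of about 6% to 33% at 50 v 200 pairs depend on assumed values of rho and d, on recruiting the maximum of 250, on a 20% quit rate and on full retention. A reader might also infer that the comparison is shown to be imprecise. The documents do not support that, because they give neither a variance nor the share of it that baseline data would explain.

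**What to change.** In section 3.2, add a second purpose for the baseline data: adjustment of between-group comparisons.

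In section 3.3, for the Quit v Smoking and e-cigarette contrasts:
- Compare each feature's within-person change (timepoint 3 minus timepoint 1) in a model adjusted for baseline smoking behaviour, age, sex, socioeconomic status and recruitment route.
- Fix these covariates before laboratory data are linked to cohort.
- Show the unadjusted result beside the adjusted one.
- Give a model that conditions on the timepoint 1 value as a sensitivity analysis only, for the reason shown in the working.
- For any classifier that separates these groups, report its gain over a model containing the covariates alone.

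The paired analysis within quitters stays as it is. The change is wording in two sections. Smoking behaviour, socioeconomic status, date of birth and gender are already collected, and route is known at recruitment; how finely the questionnaire records smoking intensity and duration is not stated and should be checked. The cost is a few degrees of freedom in a small Quit Cohort, felt most in the e-cigarette subgroups. Unmeasured confounding remains and should be acknowledged when results are reported.

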#### 3.3. Data analysis

The clinical cohort will be stratified according to smoking status at timepoint 3 into a Quit Cohort (stopped smoking for 3 months or more at the time of sample collection) and a Smoking Cohort (smoked within 3 months of sample collection). Analysis of laboratory data will be stratified over time (baseline compared to timepoint three) and according to final cohort categorisation.

Machine learning algorithms will be developed to integrate across all of the features of the multi-omics analysis of normal tissues, to identify the combinations of parameters that contribute most to cancer risk. We will integrate salient features of the dynamics of tissue perturbation by tumour promoters including the clonal structure of tissues, protein and gene expression patterns, and differences in the pattern of infiltration of immune cell populations. In order to understand the association between these features and carcinogenesis. We will study whether they can be used to discriminate between groups of samples before or after intervention. We propose an analysis that is organized in logical steps with increasing degrees of complexity.

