## PROMINENT Smoking Cessation Study

**5.4.4. Timepoint 4 (TP4)**

Participants who attend TP3 who are classified as a former smoker will be invited to attend a further appointment 3 to 6 months after TP3 (TP4). Samples collected at TP4 include the following

- Buccal swab
- Mouthwash sample
- Breath carbon monoxide measurement
- Nasal swab (optional)
- Nasal brush (optional)
- Blood sample (optional) – 50mL volume maximum

Study questionnaires will be completed by the participant, at all timepoints, either at the study visit or over the telephone (with a member of the research team recording the participant's response to questions). This can be completed electronically (an electronic device will be available on site for this purpose) or on paper.

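### Section 3.3 names no between-cohort contrast of change, so time effects shared by quitters and smokers stay in the cessation estimate, and TP4 has no stated analysis role

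*Protocol*

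**What the plan says.** Protocol section 3.3 defines the groups at TP3: "The clinical cohort will be stratified according to smoking status at timepoint 3 into a Quit Cohort" and a Smoking Cohort. It then sets the laboratory comparison: "Analysis of laboratory data will be stratified over time (baseline compared to timepoint three) and according to final cohort categorisation". The integrated features are to be used in the same way: "We will study whether they can be used to discriminate between groups of samples before or after intervention". Later in the section: "Models able to discriminate between normal tissue before and after intervention will be built and evaluated".

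The first outcome measure in section 2.2 has the same form: "Differences in molecular signals before and after smoking cessation". In section 2.1.1, continuing smokers appear as a comparator in the e-cigarette objective but not in the cessation objective.

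Two passages leave room for a comparison between cohorts. Section 3.3 begins its analysis steps with "First, we will conduct univariate group comparison analysis to assert any outstanding correlations feature-wise", without saying which groups are meant. Section 5.2.1 adds "We also aim to recruit paired samples from participants who are current smokers at baseline and at timepoint 3", with no target number.

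Section 5.4.4 and Appendix 1 provide for TP4, a further sample set from former smokers 3 to 6 months after TP3. Section 3.3 does not mention TP4.

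**The concern.** The first primary objective is the effect of cessation on normal nasal and buccal cells. In the Quit Cohort, the before/after label coincides with everything else that differs between the two visits. The protocol itself points to some of this. Section 4 allows follow-up of Lung Health Check participants to move from the truck to a hospital site or the home, and section 5.4.2 lets TP3 fall at varying intervals after baseline. Season and assay batch are ordinary further candidates, though the protocol does not discuss them.

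Stratifying by cohort gives one before-after contrast within each cohort. It does not subtract one from the other. A classifier trained on before versus after is more exposed still: it can separate samples by batch or season, and the SHAP values would then present those features as biology. At stake is whether a reported cessation signature is due to cessation or to elapsed time.

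TP4 raises a smaller matter. These samples carry the longest abstinence in the study, yet the analysis section gives them no purpose.

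**Working it through.** **1. The plan's own figure.** Section 5.2.1 wants at least 50 quitter pairs at a quit rate of about 20%. 50 / 0.20 = 250, which matches the stated maximum. The remainder, 250 − 50 = 200, is the most smoker pairs possible if everyone returns; the protocol sets no number.

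**2. Assumptions for the illustration.** The protocol gives no alpha, power, SD or drift. I take two-sided alpha 0.05, one feature at a time, drift δ in units of the SD of the within-person change, equal SD in both cohorts, and a true cessation effect of zero.

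**3. Before-after test in quitters.** A paired t test with n = 50 has noncentrality δ√50. At δ = 0.3 this is 0.3 × 7.07 = 2.12 on 49 degrees of freedom.

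| Common drift δ | Significant in quitters, n = 50 | Significant in smokers, n = 200 |
|---|---|---|
| 0.1 | 11% | 29% |
| 0.2 | 28% | 80% |
| 0.3 | 55% | 99% |
| 0.4 | 79% | about 100% |

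The nominal rate is 5%. The percentages apply to features that drift by δ, not to all features. The last column shows that a large Smoking Cohort would usually reveal the drift, but seeing it there does not remove it from the quitter estimate.

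**4. Between-cohort test of change.** The expected difference is (δ + effect) − δ = effect. With effect zero, the test holds 5% whatever the value of δ, provided δ is the same in both cohorts.

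**5. Price in precision.** The normal-approximation detectable difference at 80% power is (1.960 + 0.842) × SE = 2.80 × SE, in SD units of the change.

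| Contrast | SE | Detectable difference |
|---|---|---|
| Within quitters, 50 pairs | √(1/50) = 0.141 | 0.40 |
| 50 quitter vs 200 smoker pairs | √(1/50 + 1/200) = 0.158 | 0.44 |
| 50 vs 100 | √(1/50 + 1/100) = 0.173 | 0.49 |
| 50 vs 50 | √(1/50 + 1/50) = 0.200 | 0.56 |

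**6. Equal drift is not assured.** Under section 5.4.2 a quitter's TP3 is arranged once three months of abstinence are reached, whereas a continuing smoker's follows a status check 3 to 12 months after baseline. The TP1-to-TP3 interval can therefore differ by cohort.

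**The case against.** The strongest reply is that stratifying by time and by cohort is already a cohort-by-time layout. The smokers get the same contrast, so shared drift would be visible there. The protocol deliberately seeks smoker pairs and plans a group comparison; the study calls itself exploratory; and the model and its covariates may properly sit in an SAP that is not shown.

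Much of this stands. The text does not forbid comparing the cohorts, and the absence of a model specification is no fault. What remains is that the contrast, outcome measure and classifier target that the protocol does state are all before/after, and none of them isolates cessation.

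Three stronger readings are tempting but not supported:

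- *That the plan credits all common drift to cessation, or counts a feature when it is significant in quitters and not in smokers.* No such decision rule appears. Its error rate would also depend heavily on an unstated number. At δ = 0.3 with 50 smoker pairs it is 0.548 × 0.452 = 25%, but it falls to about 9% with 100 pairs and below 1% with 200.
- *That the TP4 samples are lost.* Section 5.6 ends the study only when all data and samples have been analysed. TP4 lacks a stated role; it is not excluded.
- *That relapse before TP4 would go unseen.* Breath CO and a questionnaire are collected at TP4 (section 5.4.4 and Appendix 1).

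Nor would the between-cohort contrast remove everything. If quitters use more nicotine replacement than continuing smokers, that is not common drift and it stays in the difference.

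**Conclusion.** The concern holds in a limited form and should be addressed. Section 3.3 names no between-cohort contrast of change, so time effects common to both cohorts are not removed from the quitter estimate, and the before/after classifiers can learn them. Under an assumed common drift of 0.1 to 0.4 SD and no cessation effect, the quitter test is significant for 11% to 79% of drifting features, against 5% for a between-cohort test of change when drift is equal. The drift sizes are assumptions, so these figures show how sensitive the stated contrast is; they do not predict the study's error rate. On TP4 the finding is only that the samples have no stated analysis role.

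**What to change.** - In section 3.3, name the Quit-minus-Smoking difference in TP1-to-TP3 change as the cessation contrast. One option is ANCOVA on the TP3 value adjusted for TP1, with the TP1-TP3 interval and recruitment source (Lung Health Check or CURE) as covariates. Because the cohorts are not randomised, ANCOVA and a simple comparison of change can disagree when baselines differ, so state which is primary.
- Train classifiers on within-person change, Quit versus Smoking Cohort, instead of before versus after.
- Give TP4 a descriptive role as persistence of change, with smoking status re-set from the TP4 questionnaire and CO. TP4 has no continuing-smoker samples, so change at TP4 cannot be corrected for drift.

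This is a change of wording and needs no sample types or visits beyond those planned. It costs the precision shown in the working, which depends on how many smoker pairs are obtained, so a target for that number would help. The contrast remains observational: people who quit may differ from those who do not in ways that adjustment does not remove.
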